### 1. PURPOSE OF STUDY (ALL AIMS/PHASES)

Infants under 6 months of age are at increased risk of both influenza (flu) and pertussis disease, and pregnant women who get influenza are more likely than non-pregnant women to have serious complications, including hospitalizations, death, preterm labor and premature birth. The Advisory Committee on Immunization Practices recommends that women receive a flu vaccine in flu season, and tetanus toxoid, reduced diphtheria toxoid, acellular pertussis (Tdap) vaccine during each pregnancy (ideally between 27-36 weeks) to lower the risk for flu and pertussis disease for both themselves and their infants. However, only half of pregnant women in the US receive a flu and Tdap vaccine, respectively; only 33% of women receive both vaccines. Lack of vaccination stems from a combination of patient (lack of knowledge, vaccine hesitancy), provider (suboptimal communication skills, missed opportunities), and system (e.g., lack of standing orders and patient reminders) factors. An effective intervention is needed to improve flu and Tdap vaccination rates for pregnant women.

This multi-site project has four key aims/phases. **Aim/Phase 1** is to measure baseline flu/Tdap vaccination coverage and provider knowledge, attitudes and behaviors for flu/Tdap vaccination in participating OB/GYN practices within 4 health systems in New York and California. **Aim/Phase 2** is to use a clustered randomized controlled trial (RCT) (practice-level randomization) to measure the effect of a multi-component quality improvement (QI) intervention (VAX-MOM: training in communication, provider prompts, standing orders + feedback on rates) on vaccination rates and provider attitudes, and to measure costs of the intervention. **Aim/Phase 3** is to develop a translational plan/toolkit for OB/GYN practices and health systems for maternal vaccination.

### 2. BACKGROUND AND RATIONALE (ALL AIMS/PHASES)

#### **Burden of flu disease and pertussis**

Infants <6 months of age are more likely than any other age group to have flu complications that lead to hospitalization. Our group has shown that the average annual rate of hospitalization attributable to flu was 4.5 per 1000 among children 0 to 5 months of age.

[figure not shown]
Flu infection rates are similar in pregnant women to the general population, but pregnant women are at higher risk of severe flu complications, including hospitalization and death and are at increased risk of adverse perinatal and neonatal outcomes. According to CDC, from 1990–2016 infants <1 year of age consistently had the highest reported annual incidence of pertussis as well as the greatest risk for serious disease and death from pertussis. Recently in the U.S., infants in the first 6 months of life had an age-specific pertussis incidence of 78 per 100,000; 43% of those with reported infection were hospitalized. While infants start DTaP vaccine at 2 months and vaccination rates are high, they are not well protected until they complete their primary series at 6 months of age.

### **Effectiveness of maternal vaccination**

A 2016 systematic review showed that maternal flu vaccination provided “substantial benefit for infants and mothers,” with reduced rates of preterm birth and low birth weight. Infants <6 months of age whose mothers had received flu vaccine had a 63% reduction in laboratory-confirmed flu and a 29% reduction in respiratory illness with fever compared with controls; mothers had a reduction of 36% in the rate of respiratory illness with fever. Maternal flu vaccination is 91.5% effective in preventing flu-associated hospitalization in newborns. In a cohort study of mother-infant pairs, the rate of pertussis was 43% lower among infants whose mothers received prenatal Tdap than among infants whose mothers did not; protection was seen only among infants whose mothers received Tdap at >27 weeks of gestation. These findings are consistent with earlier studies that showed maternal vaccination was associated with higher cord serum concentrations of pertussis antibodies and, that maternal Tdap receipt at 30-32 weeks gestation was associated with significantly higher infant serum concentrations of Tdap antibodies at birth and 2 months of age.

### **Barriers to Vaccination**

There are many barriers to influenza and Tdap vaccination for pregnant women. Our team has conceptualized these barriers into a widely used model; the VAX-MOM study will address multiple components by focusing on provider and staff communication, prompts and/or standing orders, provider feedback, and patient education/reminders to overcome these barriers (Figure 1).

[figure not shown]

Patient Barriers include vaccine hesitancy, lack of knowledge of the benefits and risks of flu or Tdap vaccine or protection for the baby, concerns about vaccine safety generally and during pregnancy, low perceived susceptibility to infection, and lack of access.

Vaccination rates are lower for younger women, Blacks, those with public insurance, lower income, and inadequate prenatal care. Provider Barriers include missed opportunities for vaccination, lack of a vaccine recommendation or weak endorsements by health providers about needed vaccines (the most important predictor in many studies), various suboptimal practice operations, insufficient knowledge, financial barriers, and lack of reminder recall. System Barriers include the lack of a tracking or reminder system, as well as suboptimal staff training, and challenges with vaccine purchase and storage.

### 3. ADMINISTRATIVE ORGANIZATION (AIM/PHASE 2 ONLY)

**NOTE:** As stated at the onset of the protocol, we are requesting that the University of Rochester RSRB serve as the IRB of record for all study sites during aim/phase 2 of the study. **The remainder of the protocol will describe aim/phase 2 details only.**

### STUDY SITES & PROJECT STAFF OVERVIEW

[REDACTED], study PI, will ensure study and regulatory compliance, by:

- Participating in routine prescheduled meetings with all project investigators and project staff for the duration of the study, including:
  - *Weekly Core Leadership Team Meetings* (State-level Investigators, study coordinators, all study consultants, data specialist): discussion of global project goals, timeline, regulatory requirements and adherence, protocol requirements and adherence, measure development, e-learning content, data analysis, workflow details, etc.

- *Weekly State-level Team Meetings* (State-level Investigators, study coordinators, data specialist as needed): discussion of day-to-day operations needed to support global study goals (including protocol and regulatory items).
- *Weekly Site-level Team Meetings* (State-level Investigators, study coordinators, Site Investigators, OB/GYN site liaisons, site EHR report builders): discussion of provider/nurse workflow, development of study measures specific to providers/nurses, optimal measure dissemination procedures, identification of possible vaccine champions.
- *Data Development & Analysis Meetings* (State-level Investigators, study coordinators, EHR report builders, data specialists): discussion of data collection methods, EHR data extraction methods, data analysis, data storage/management.
- Keeping all study personnel abreast of *prearranged study changes* and subsequent regulatory determinations (e.g., changes to study measures, workflow procedures, study personnel, etc.) via a predetermined communication chain:
  - Core Leadership Team discusses necessary study change → NY study coordinator submits amendment to RSRB → RSRB notifies Study PI and NY study coordinator of regulatory determination → Study PI and NY coordinator notify Core Leadership Team → As appropriate, both study coordinators will further notify site-level personnel and/or data specialists
  - Communication with study site personnel will most often take place during prescheduled meeting times, but in more urgent cases, will take place as soon as needed.
  - Communication will be both verbal (during or outside of weekly meetings depending upon level of urgency) and written as needed (via e-mail, e-mail attachments, or the secure shared Box folder).
- Keeping all study personnel abreast of *unforeseen study events* and subsequent regulatory determinations (e.g., protocol deviations, breaches in confidentiality, subject/site withdrawal, etc.) via a predetermined communication chain:
  - Study personnel reports study event to PI → PI notifies NY study coordinator → PI and NY study coordinator notify RSRB, as well as other study personnel as appropriate → any action requested by RSRB is communicated to Core Leadership Team → As appropriate, both study coordinators will further notify site-level personnel and/or data specialists
  - As described above, communication will be both verbal and written.
  - Also see section #16 “Data & Safety Monitoring Plan”

#### 4. STUDY DESIGN & PROCEDURES (AIM/PHASE 2 ONLY)

##### **Brief Overview of Aim/Phase 2:**

Using a clustered RCT (randomizing practices), we will allocate half of the practices within each health system to the VAX-MOM intervention and the other half to standard of care. We will measure the impact of the intervention on vaccination rates (primary outcomes) and missed opportunities and process metrics (secondary outcomes) (see Table 4). Finally, if VAX-MOM is successful, we will provide the control practices the intervention during Year 3.

##### **Design and Procedural Details of Aim/Phase 2:** (also see Figure 2 for Timeline)

###### **Step 1) Deliver VAX-MOM training/intervention to randomized practices:**

###### Randomization Details:

Practices will be the unit of randomization. We will assign practices using a covariate constrained randomization strategy as follows: First, we will use data from Aim #1 to obtain key factors that we expect to affect the primary outcomes. We will perform constrained randomization to allocate practices within each health system to intervention/control arms and ensure each arm has similar baseline flu and Tdap vaccination rates, percent of patients covered by Medicaid, number of OB providers, and number of patients. Specifically, we will use these variables to construct and evaluate a balance criterion, which is the sum of the squared difference between standardized group means on these variables. We will generate randomization separately by health system. We will generate all possible combinations of eligible practices in 2 arms (using a SAS macro), and define an acceptable set of randomizations that result in balanced variables (generally the lowest 10% on the balance criterion). From this set of randomizations, we will select one set at random, and then randomly assign each practice to intervention vs control group.

###### Intervention Details:

Once randomization has been completed, and “intervention group” practices have been identified, multiple quality improvement (QI) techniques will be aimed at practice providers, nurses, and staff.

- **Identification of “vaccine champion” at each intervention site:** At each site, the affiliated medical director will select one “vaccine champion” for the practice. Each identified vaccine champion will be e-mailed an Information Sheet (see “*InformationSheetVaccineChampion...*” document) by their affiliated study coordinator, outlining the basic study goals as well as their involvement in tasks throughout the training and intervention adoption phases of the study (see “Consent Process” section). The position of vaccine champion is voluntary, and if they do not wish to accept the role, they may decline and another individual will be identified by the affiliated medical director. The vaccine champion will play a lead role throughout the study intervention, including:

- assisting with the dissemination of e-learning training modules and the scheduling of a follow-up site-specific meeting
- acting to ensure training content is being appropriately adopted into practice workflow procedures
- fielding questions from site personnel regarding the logistics of study interventions
- acting as an ongoing liaison between the site personnel and study staff
- leading bi-monthly discussions regarding immunization rate feedback with site personnel (see step 2 for further detail)
- planning for and completing monthly PDSA cycles (see step 2 for further detail)
- monthly completion of the “Practice Time/Cost Survey” (see step 4 for further detail)

- **Delivery/discussion of training modules:** Each site will receive training focused on 3 main areas of content (see Table 3). This training will be delivered first via an online e-learning platform, and next via an in-person or virtual site meeting.

**Table 3: Training Module Content**

Training Topic:	Training Content Details:
Flu & Pertussis 101	General information regarding prevalence/severity of influenza and pertussis disease
	General information regarding benefits of flu/Tdap vaccination
	Benefits of flu/Tdap vaccination within the pregnant population (e.g., benefits of passive immunity)
Communication	Understanding and applying a “Presumptive Recommendation”
	Brief introduction to Motivational Interviewing (MI) and application with vaccine hesitant pregnant women
	Communication Tips & Tricks: Responses to common concerns/questions about vaccines
Optimizing Office Workflow	Optimal methods and organizational/tracking tools
	

• Pre-visit planning and nurse prompts

	

• EHR prompts (Checklists/Text Fields)

	

• Standing orders

	

• Vaccine rate feedback

	

• Vaccine champion and utilization of PDSA cycles

	

• Optimal vaccine documentation (e.g., vaccines given offsite)

	Putting it all together
	

• “Teamwork”- Ensure entire multidisciplinary team trained in utilization of new methods/tools

	

• “Consistency”- Ensure all tools/methods used consistently

	

• “Adjust as Needed”- Use feedback reports & PDSA cycles to reflect on progress and fine-tune accordingly

- **E-learning platform:** Module content will first be disseminated to practice site personnel via an online e-learning platform (i.e., Articulate). Study coordinators will obtain e-mail addresses for the site personnel from either the health system liaison or the associated vaccine champion, and will then e-mail a training content link to all appropriate site providers, nurses, and staff. Attached to this initial e-mail will be an Information Sheet describing the study goals and training phase details, as well as their involvement throughout the duration of the 12-month QI intervention (see “*TrainingPhaseEmail...*” and “*InformationSheetTrainingPhase...*” documents; also see “Consent Process” section for more detail). After reviewing the Information Sheet and discussing any questions/concerns with study staff, site personnel will be asked to access and complete the training lessons prior to their scheduled site meeting.

Embedded at the conclusion of the online training module, will be a link to a brief REDCap survey (see “*TrainingModuleCompletionSurvey...*” document) to obtain information regarding those who have fully completed the training. A list of practice personnel who have successfully completed the online training will be stored in a password-protected Excel/Word file by each study coordinator. The names will not be linked with any other study data. The list will be accessible only by study staff for the purposes of confirming those who should receive CME/CNE credit.

Note: For intervention sites that have completed the e-learning training during the first half of the calendar year (i.e., prior to July), site personnel may be asked to additionally complete an abbreviated “flu booster” e-learning module just prior to flu season of that same year (e.g., in Aug/Sept). This abbreviated version (approx. 15 minutes to complete) will contain content (see table 3) only applicable to influenza.

- **Site Meeting:** Following the online training, all site personnel will meet with study staff either in-person or via a virtual Zoom meeting. The meetings (both virtual and in-person) will be audio and video recorded using a laptop or handheld recording device (in-person meetings) or via the Zoom recording option (virtual meetings) (see “Audio/Video Recording” and “Privacy and Confidentiality” sections for more detail). These archived video files will allow for the review of meeting content by site personnel who were unable to attend the meeting live, or by those who simply wish to review the meeting discussion for a second time.

During the site meeting, study staff will briefly review online training content, allow time for the sharing of comments/questions from site personnel, and lead a discussion regarding the application of training content ideas specifically to that practice site. During this meeting, study staff will also present site personnel with their current immunization rates.

Each designated vaccine champion will track meeting attendance, and a list of practice personnel who have attended the site meeting will be e-mailed to the study coordinators and stored in a password-protected Excel/Word file. The names will not be linked with any other study data. This list will be accessed for the purposes of confirming those who should receive MOC credit.

Note: For intervention sites that have completed their site meeting during the first half of the calendar year (i.e., prior to July), site personnel may be asked to participate in a second abbreviated “flu booster” site meeting just prior to flu season of that same year (e.g., in Aug/Sept). This abbreviated meeting (approx. 15 minutes) will discuss content (see table 3) only applicable to influenza.

- **MOC/CME/CNE Credit:** To encourage the completion of online trainings and the attendance at site meetings, providers and nurses will be offered CME/CNE credit for completing learning modules, and MOC/QI credit for attending office systems change meetings and reviewing practice rates.

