**Table 4: Summary of Outcome Measures and Tools**

RE-AIM Category	Outcome Measure(s)	Data Source
Reach	
 
Number of patients seen in the practice within study period.
 
Number of providers/nurses/staff completing the training modules.
 
	EHR data & training attendance records
Effectiveness	
 
Primary Outcome: Rate of flu and Tdap vaccination
 
Secondary Outcomes: Flu and Tdap vaccination rates by subgroups including (i) insurance groups, (ii) race/ethnicity, (iii) number of pregnancy, (iv) flu vaccine in prior year
 
	EHR data
Adoption	
 
Missed opportunities by (i) provider characteristics and (ii) patient characteristics
 
Number and proportion of personnel involved in the VAX-MOM office changes (receiving MOC credit, attending in-office meetings)
 
	Provider Surveys, EHR data, training attendance records
Implementation	
 
Provider and office staff perceptions of feasibility, acceptability, barriers and facilitators to implementation, adherence to intervention, perceived time and cost, and impact on patient flow.
 
Missed opportunities for flu/Tdap vaccination.
 
Perceived strength of vaccine recommendations.
 
Perceived adherence to staff checking whether flu/Tdap is due.
 
Costs of implementing interventions
 
	Provider Surveys, EHR data & *Time/Cost Survey
Maintenance	
 
Sustainability
 
	Provider Survey

\*See Step 4 for more details

Details for EHR data extraction:

- Measure Description (also see “*EHRDataExtraction ...*” document)  
We will work with our experienced [REDACTED] analysts (initial planning of required data fields and subsequent analysis of data output) and health system report builders (algorithm development) to extract EHR data for the purposes of evaluating basic flu and Tdap vaccination rates and additional secondary outcomes (see Table 5).

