**Table 5. EHR Data Extraction Categories**

Primary	

• Flu vaccines received during flu season (Sept-April)

• Tdap vaccines received during 27-36 weeks of pregnancy

Secondary	

• Vaccine refusal (as documented in EHR)

• Missed opportunities for flu and Tdap

• Flu vaccine in prior season

• Covid vaccination

Patient Demographics	

• Race/ethnicity

• Age

• Insurance

• Language

• Parity

Practice Demographics	

• Site

• Provider type (resident, midwife, MD)

- Measure Procedures

Each health system [REDACTED] will have its own “report builder.” The report builder will be in charge of collecting the electronic health record (EHR) data from their own health system and putting it into a format (report) that can be easily understood and analyzed by study staff.

*Bi-Monthly Feedback Reports:* The report builder for each health system will create vaccine rate feedback reports utilizing extracted EHR data for intervention sites on a bi-monthly basis. These reports will be sent either via secure e-mail directly to the study coordinator in each corresponding state, or uploaded to the secure shared Box folder. The study coordinator will then disseminate the vaccination rates for each site to all corresponding site personnel.

For NY health systems, in the event an automated EHR feedback report cannot be generated in time for any given month, the identified vaccine champions or study personnel will estimate flu and Tdap vaccine rates via manual chart review. All vaccine champions and/or study personnel conducting manual chart review will have completed all appropriate eRecord training prior to accessing patient charts. Of those patients who delivered during the identified month, at least 20% will be reviewed. For each chart reviewed, the vaccine champion or study personnel will document the receipt (or lack thereof) of influenza and Tdap immunization as well as Covid vaccination when possible, and will share results with the study team via secure e-mail.

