*Final EHR Data Analysis:* Additionally, at the conclusion of aim/phase 2 (12-month duration) each health system report builder will create a final EHR report for both the intervention sites as well as the control sites capturing updated baseline information from 2019 and 2020 (now needed due to COVID pause), as well as detailed intervention information from 2021 and 2022 (information indicated in Table 5 that was not captured during monthly reports). These final reports will be uploaded to a shared folder on the secure Box platform, accessible by select study staff [REDACTED].

[REDACTED] This report will allow for the comparison of vaccination rates and secondary outcomes

between intervention and control sites. In the event that the final automated EHR reports cannot be generated in a timely manner by the report builders, study personnel and/or a medical student (after being added to the study protocol) will conduct manual EHR chart reviews to collect the data. They will be appropriately trained in the EHR system requiring access, prior to conducting the chart reviews.

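### Only intervention practices are trained to chart off-site vaccines, and both co-primary outcomes are read from the chart, so part of any difference may be recording; the visible analysis plan does not separate the two.

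*Combined protocol and SAP*

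**What the plan says.** - **Allocation.** Section 4 (Brief Overview): "we will allocate half of the practices within each health system to the VAX-MOM intervention and the other half to standard of care". Controls are offered the intervention only in Year 3, and only if it succeeds.
- **Training.** Section 4, Intervention Details, describes what happens once the intervention practices have been identified: "Each site will receive training focused on 3 main areas of content (see Table 3". In that context each site means each intervention site. Under office workflow, Table 3 lists "Optimal vaccine documentation (e.g., vaccines given offsite". A vaccine champion at each intervention site has the task of "acting to ensure training content is being appropriately adopted into practice workflow procedures".
- **Outcome source.** The text after Table 4 says analysts and report builders will "extract EHR data for the purposes of evaluating basic flu and Tdap vaccination rates". Table 5 names the flu item as "Flu vaccines received during flu season (Sept-April", and Tdap as doses received at 27-36 weeks. It shows no field for where a dose was given.
- **Final extraction.** Final EHR Data Analysis describes a "final EHR report for both the intervention sites as well as the control sites capturing updated baseline information from 2019 and 2020", plus 2021 and 2022. If automated reports are late, study personnel "will conduct manual EHR chart reviews to collect the data".
- **Verification.** Section 14 has staff check a small percentage of patient files against the EHR reports.
- **Analysis.** Section 17 specifies a log-link binomial mixed model per vaccine. It adjusts for the practice-level balancing variables and race/ethnicity and, for flu, prior-year vaccination. The subgroups in Table 4 do not include dose source.

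**The concern.** One arm is trained to make the outcome record more complete, and the other is not. A dose given at a pharmacy or another clinic counts only if someone enters it. If training raises that entry rate, recorded coverage rises in the intervention arm even if no additional woman is vaccinated.

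Randomisation and adjustment for baseline rates do not remove this, because the change in charting starts after allocation and in one arm only. The verification step and the manual fallback may find a dose charted where the report does not look, but not one that was never charted.

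The stake is interpretation. The outcome is worded as vaccines received, and Section 17 uses the same rates as the effectiveness measure for cost per additional vaccination. A dose that would have been given anyway and is merely newly charted is not an additional vaccination. Counting it makes the ratio look more favourable.

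**Working it through.** **1. The plan's own figure (Section 17).** Inputs: control rate 49%, ICC 0.01, two-sided alpha 0.025, and 5,000 women in 16 practices, read as per arm (the reading that reproduces the stated power).
- Cluster size 5,000/16 = 312.5; design effect 1 + 311.5 × 0.01 = 4.115.
- SE = √(2 × 0.49 × 0.51 × 4.115 / 5,000) = 0.0203.
- Detectable difference at 80% power = (2.241 + 0.842) × 0.0203 = 6.25 points, which agrees with the stated 6.3.

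**2. Tdap artefact with no true effect.** Assumed, because the documents give none of these: true coverage 55% in both arms; off-site share of doses *o*; charting of off-site doses *c0* in control and *c1* in intervention.
- Artefact d = 0.55 × o × (c1 − c0).
- Two-sided rejection chance = 1 − Φ(2.241 − d/0.0203) + Φ(−2.241 − d/0.0203), against a nominal 2.5%.

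| Off-site share | Charting, control to intervention | Artefact (points) | Rejection chance |
|---|---|---|---|
| 10% | 50% to 70% | 1.1 | 4.7% |
| 10% | 50% to 90% | 2.2 | 12% |
| 20% | 50% to 70% | 2.2 | 12% |
| 30% | 50% to 70% | 3.3 | 27% |
| 20% | 50% to 90% | 4.4 | 47% |
| 30% | 50% to 90% | 6.6 | 84% |
| 10% | gain of 5 points | 0.3 | 2.6% |
| 30% | gain of 10 points | 1.7 | 7.8% |

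These are normal approximations. A t reference with 30 degrees of freedom lowers the 84% to about 81%.

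**3. Flu under the planned log link.** Further assumptions: prior-year coverage 50%, and current uptake 80% or 30% by prior status (0.5 × 0.80 + 0.5 × 0.30 = 55%). A dose is recorded with probability r = 1 − o + o × c.
- *Prior-year charting changes in the same way.*
  - Largest case (30% off-site, 50% to 90%): r goes from 0.85 to 0.97.
  - Among women with a recorded prior dose, recorded uptake is 0.80 × 0.85 = 0.680 in control and 0.80 × 0.97 = 0.776 in intervention, a ratio of 1.141.
  - Among the rest it is 0.85 × 0.21/0.575 = 0.310 and 0.97 × 0.162/0.515 = 0.305, a ratio of 0.983.
  - A log-binomial fit to these expected cells gives a common risk ratio of 1.113. On a recorded control rate of 0.55 × 0.85 = 46.75%, that is 5.3 points.
  - Smallest case (10% off-site, 50% to 70%): risk ratio 1.017 on 0.55 × 0.95 = 52.25%, or 0.9 points.
- *Prior-year field unaffected*, for example because those doses predate the training. The risk ratio is r1/r0: 0.97/0.95 = 1.021 to 0.97/0.85 = 1.141. This is the same 1.1-6.6 points as for Tdap.

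**4. What a practice-only count would show.**
- With 10-30% of doses off-site it reads 0.55 × 0.90 = 49.5% down to 0.55 × 0.70 = 38.5%, instead of 55%.
- If 20% of doses are off-site and a fifth of those move on-site with the total unchanged, it shows 0.55 × 0.20 × 0.20 = +2.2 points.

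**The case against.** - **Off-site charting is a single example within a multi-component programme.** Prompts, standing orders and communication training aim at real receipt, and sites choose their own PDSA activities. This stands: a real effect is possible, and charting may change little. A reader might infer that a positive result would be mostly recording, or that the design is invalid. The documents support neither.
- **Other data bear on the question.** PDSA logs, observation of a subset of New York intervention sites, the Provider & Nurse Survey in both arms, and extracted refusals and missed opportunities may show whether charting practice changed. This stands, but none of them splits doses by source.
- **Dose source may already be defined.** The protocol refers to a separate EHRDataExtraction document that is not available here, so it cannot be said that the trial lacks the field. Nor do the documents say how off-site doses reach the record; any automatic feed would shrink the artefact.
- **The flu covariate corrects itself.** A reader might infer that prior-year adjustment cancels or even reverses the flu artefact. The documents do not say that training changes prior-year charting. Even if 60% of prior-season and 20% of current doses are off-site and charting rises from 50% to 80% for both, the planned log link gives a risk ratio of 1.028, about +1.4 points.
- **The inputs are assumed.** This is correct, and it limits the verdict. The 84% is the extreme of the grid and needs a 40-point charting gain across the arm.

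**Conclusion.** The concern holds in a limited form. One arm is trained to improve recording of the outcome, both co-primary outcomes come from that record, and the visible analysis plan does not separate recording from receipt.

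The size is undetermined: on the assumed inputs it runs from well under one point to about the full design effect. For flu it depends on whether the prior-year field is affected too (about 0.9-5.3 points if it changes in the same way, 1.1-6.6 if it does not). These figures illustrate what is possible and do not estimate what will happen.

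This is a cheap improvement to interpretation, of modest severity. The power calculation is not at fault, and the primary analysis need not change.

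**What to change.** Unless the EHRDataExtraction document already provides for it:

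1. Add dose source (given at the practice, or an outside/historical entry) to the final extraction in both arms, where retrievable. Any manual-review fallback should collect the same field.
2. Keep the primary analysis unchanged. Pre-specify, as a sensitivity analysis, the same model counting only practice-administered doses.
3. Report practice-administered and off-site-documented rates by arm for 2019-2020 and 2021-2022, periods the final report already covers.
4. Show the flu model with and without the prior-year covariate.
5. State that the split shows where a difference arises and does not by itself prove receipt or recording.
6. Where a health system cannot retrieve dose source, report that as a limitation.

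**Cost.** A small amount of extra extraction and analysis, arranged with the report builder in each of the four health systems. The practice-only count understates coverage, can miss real off-site gains and can be inflated by doses moving on-site, so it should remain a sensitivity analysis.
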